### 8.2.2 Recording of Adverse Events

All adverse events will be coded by system organ class and preferred term using the Medical Dictionary for Regulatory Activities (MedDRA) (version effective at trial start).

During each clinical follow-up, the Investigator or Investigator designee will determine AE occurrences. Each adverse event is considered to be either anticipated or unanticipated as described above. The site is required to report all adverse events that occur during the trial. AEs will be collected from the time of informed consent until the final follow up.

Post-treatment outcomes that are evaluated as efficacy endpoints, such as pain on weight-bearing, harvest site pain, etc., will not be reported as AEs. Post-operative pain is, in general, anticipated, typically improves over time, and it will not be considered an AE. However, surgical site pain that is associated with a complication, or worsens over time, may be considered an AE.

Any abnormal laboratory test results or other safety assessments (e.g., vital signs measurements, etc.) considered to be clinically significant in the medical and scientific judgment of the Investigator are to be recorded as AEs.

The sign and symptoms and/or clinical sequelae resulting from lack of efficacy will be reported if they fulfill the definition of an AE or SAE.

Internal fixation medical devices (e.g., screws, plates, pins and staples) are being used in this study and are considered ancillary devices. Medical device events associated with these ancillary devices, including those resulting from screw loosening or malfunctions of the ancillary device, must be documented and reported as adverse events by the Investigator throughout the study.

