2.2 Endpoints

2.2.1 Primary Endpoint

The primary efficacy endpoint is the proportion of subjects who meet all the following criteria for the Subject Performance Composite (SPC) Endpoint at 52 weeks:

- Improvement in pain on weight-bearing at fusion site (≥ 20 mm reduction from baseline on 100 mm VAS)
- Absence of significant graft harvest site pain (< 20 mm on 100 mm VAS)
- Improvement in Foot and Ankle Ability Measure Activities of Daily Living subscale (FAAM-ADL) (≥ 8 points improvement from baseline)
- Absence of device related or procedure related SAEs (up to Week 52)
- Absence of secondary surgical or nonsurgical interventions intended to promote fusion (up to Week 52)

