9.1 General Considerations

Non-inferiority tests will be conducted at a one-sided 5% significance level whereas superiority tests will be conducted at a two-sided 5% significance level per an agreement with the FDA in the AMPLEX IDE.

All efficacy analyses will be conducted for the mITT analysis set unless specified otherwise. The primary and key secondary efficacy endpoints will be analyzed by a fixed-sequence procedure according to the following order to maintain the overall Type 1 error rate to a one-sided 5% for non-inferiority and a two-sided 5% for superiority testing.

- 1) Non-inferiority of AMPLEX to ABG in the primary efficacy endpoint (primary analysis)
- 2) Non-inferiority of AMPLEX to ABG in the key secondary efficacy endpoint
- 3) Superiority of AMPLEX to ABG in the key secondary efficacy endpoint
- 4) Superiority of AMPLEX to ABG in the primary efficacy endpoint

Testing procedure will begin with the non-inferiority test for the primary efficacy endpoint, and each test will be conducted without adjustment of multiplicity as long as all preceding tests are significant. All other secondary endpoints will be presented with the point estimate of the treatment group difference and the corresponding 2-sided 90% and 95% confidence intervals.

For visit-based data, the data collected on the day that is closest to the scheduled trial day within a window specified in Table 1 will be assigned to the corresponding analysis visit. If the closest day cannot be uniquely identified for an analysis visit, the data collected on an earlier trial day will be assigned to the analysis visit. Visit windows for the analysis are specified in a way to utilize all collected data as much as possible and are different from the protocol specified visit windows.

Table 1 Scheduled trial day and window for analysis visits

Analysis visit	Scheduled trial day	Analysis window
Baseline	Day -84 to Day 1	Up to prior to the initiation of surgery
Post-Operative CT and X-ray	Day 1	Day 1 to Day 29
Week 2	Day 15	Day 2 to Day 29
Week 6	Day 43	Day 30 to Day 64
Week 12	Day 85	Day 65 to Day 127
Week 24	Day 169	Day 128 to Day 267
Week 52	Day 365	Day 268 to Day 456
Week 78	Day 547	Day 457 to Day 637

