9.2 Primary Endpoint

9.2.1 Primary Variable Analysis

The primary efficacy endpoint will be the proportion of subjects who meet all of the following criteria for the SPC at 52 weeks:

- Improvement in pain on weight-bearing at fusion site (≥ 20 mm reduction from baseline on 100 mm VAS)
- Absence of significant graft harvest site pain (< 20 mm on 100 mm VAS)
- Improvement in Foot and Ankle Ability Measure Activities of Daily Living subscale (FAAM-ADL) (≥ 8 points improvement from baseline)
- Absence of device related or procedure related SAEs (up to Week 52)
- Absence of secondary surgical or nonsurgical interventions intended to promote fusion (up to Week 52)

The primary analysis will assess a non-inferiority of AMPLEX to ABG, and it will be claimed if the lower bound of the 2-sided 90% CI for the difference of the proportions (AMPLEX minus ABG) is greater than -12.0%. The superiority will be claimed if the lower limit of the 2-sided 95% CI is greater than zero. The CI will be constructed with the normal approximation to the binomial. In addition, the response status for each component will be summarized.

A subject will be considered an SPC success if he/she meets all of the SPC criteria, otherwise, the subject will be considered an SPC failure. The SPC response status will be determined for 12, 24, and 52 weeks. The response status for the visit-based components (i.e., weight-bearing pain, graft harvest site pain, and FAAM-ADL) will be assessed for each time point based on the windowed analysis visits. The response status for the non-visit-based components (i.e., absence of device or procedure related SAEs and secondary interventions to promote fusion) will be assessed in a period up to the actual visit date that the corresponding visit-based variables for a particular analysis visit are collected. If the actual visit dates among the visit-based variables are different at the analysis visit, the latest visit date among them will be used to determine the period for the assessment of the non-visit-based variables. If any of the components of the SPC at an analysis visit is missing, the SPC response status will be considered missing for the analysis visit. Note that the graft harvest site pain will be collected only for the ABG group, and therefore, no data for this component will be recorded for the AMPLEX group.

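### The Week 52 event components stop at the actual assessment date, so an event recorded after an early visit but by Day 365 is not counted

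*SAP*

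**What the plan says.** Two of the five components of the primary composite (SPC) are dated events. SAP 2.2.1 and 9.2.1 state them as "Absence of device related or procedure related SAEs (up to Week 52") and "Absence of secondary surgical or nonsurgical interventions intended to promote fusion (up to Week 52"). The protocol has the same wording (sections 2.2.1 and 9.6.2).

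SAP 9.2.1 then gives the counting rule: these components "will be assessed in a period up to the actual visit date that the corresponding visit-based variables for a particular analysis visit are collected". If pain, FAAM-ADL and harvest-site pain were collected on different days, "the latest visit date among them will be used to determine the period for the assessment of the non-visit-based variables".

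SAP 9.1, Table 1, sets Week 52 at Day 365 with an analysis window of "Day 268 to Day 456". Within that window the SAP takes "the data collected on the day that is closest to the scheduled trial day within a window specified in Table 1", and on a tie the earlier day. The protocol's own visit window is Day 365 ± 30 (section 7.1, Table 3).

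SAP 9.3.1 uses the same rule for the key secondary CT endpoint: secondary interventions are counted up to the date of the CT.

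Event collection continues well beyond Week 52. Protocol 8.2.2 says "AEs will be collected from the time of informed consent until the final follow up", and the last visit is at Week 78.

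**The concern.** The pain and function scores exist only on the day they are collected, so a window is needed to assign them to Week 52. SAP 9.1 justifies its wide windows as a way to use as much collected data as possible. That reason does not apply to SAEs and interventions, which carry their own dates and are recorded whether or not a visit takes place.

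Tying the event cut-off to the visit date has two results. A subject seen before Day 365 is scored free of an event that the database shows happened before Day 365. A subject seen after Day 365 is exposed to the failure components for longer than 52 weeks. Exposure to failure therefore varies with appointment timing, in both confirmatory endpoints. Investigators are not blinded, and subjects are blinded only until after the procedure (protocol 3.4.3), so equal visit timing in the two arms cannot be taken for granted.

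**Working it through.** **1. Day arithmetic.** Surgery is Day 1, so Day 365 is 364 days later, exactly 52 weeks. Day 268 is 267/7 = 38.1 weeks and Day 456 is 455/7 = 65 weeks. The uncounted period before Day 365 is 365 − 335 = 30 days for the earliest visit inside the protocol window, and 365 − 268 = 97 days at the edge of the analysis window. Late visits add 395 − 365 = 30 days, or 456 − 365 = 91 days.

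**2. Does it happen under the ordinary schedule?** Take a subject assessed on Day 340, inside the protocol window, who meets the pain and FAAM-ADL criteria and has a procedure related SAE on Day 355. Protocol Table 3 schedules no pain VAS, FAAM-ADL or CT after Week 52, so no planned later assessment moves the cut-off. If all other criteria are met, the subject is an SPC success.

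**3. Does anything else in the SAP catch it?** No. The missing-data analyses in SAP 9.2.2 act only on subjects whose Week 52 status is missing, and this subject's is not. The ITT, PP and as-treated analyses repeat the same derivation. There is no fixed-day cut-off and no analysis that varies it.

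**4. Size per subject.** The documents give no event rates for these components, so one-year risks R of 5%, 10% and 15% are assumptions, as is a constant hazard. Counted risk for a visit on Day d is 1 − (1 − R)^(d/365). For R = 10% and d = 335: 1 − 0.9^(0.918) = 9.2%, so 0.8 points go uncounted.

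| R by Day 365 | Day 268 | Day 335 | Day 395 | Day 456 | Uncounted, Day 335 | Uncounted, Day 268 |
|---|---|---|---|---|---|---|
| 5% | 3.7% | 4.6% | 5.4% | 6.2% | 0.4 | 1.3 |
| 10% | 7.4% | 9.2% | 10.8% | 12.3% | 0.8 | 2.6 |
| 15% | 11.2% | 13.9% | 16.1% | 18.4% | 1.1 | 3.8 |

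These are component risks. The change in SPC success is smaller, because some of these subjects fail on pain or function anyway.

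**5. Effect on the comparison.** If visits scatter evenly around Day 365, early and late visits nearly cancel (−0.8 and +0.8 points at R = 10%). If one arm is seen 30 days earlier on average (Day 335 against Day 365), the component differs by 0.4, 0.8 or 1.1 points. Timing can also be equal while event rates differ. With everyone seen on Day 335 and risks of 5% and 15%, the arm with more events gains 1.1 − 0.4 = 0.7 points.

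**6. Effect on the test.** First, the plan's own figure. For margin 12%, rates 60% and 62%, one-sided 5%, 85% power and 2:1 allocation: n(ABG) = (1.645 + 1.036)² × (0.60×0.40 + 0.62×0.38/2) / (0.12 + 0.02)² = 7.19 × 0.3578 / 0.0196 = 131.2, so 132, and 396 in total as stated. With the same variance formula at the margin (ABG 60%, AMPLEX 48%, 132 and 264 subjects), SE = √(0.24/132 + 0.2496/264) = 5.26 points. A net shift in SPC success of 0.5 or 1 point favouring AMPLEX raises the one-sided error from 5.0% to about 6.1% or 7.3%. A shift favouring ABG lowers it.

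**The case against.** The best defence is that the SAP already limits the problem. It takes the assessment closest to Day 365, not any assessment in the window. A Day 268 assessment would stand as Week 52 only if nothing were collected from Day 269 to Day 456. It would also need a Week 52 visit 67 days before the protocol window opens (335 − 268), or a Week 24 visit 69 days after its window closes (268 − 199). Protocol 4.2.1 asks for missed visits to be made up as soon as possible, which pushes dates later. All of this stands: Day 268 to 456 is the permitted range, not the expected one, and most gaps should be 30 days or less.

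A reader might infer that the SAP contradicts the protocol endpoint. The documents do not support that. Neither one defines *up to Week 52* as Day 365, and reading it as the Week 52 visit, itself scheduled at ± 30 days, is a legitimate definition.

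A reader might also infer that the rule only creates false successes, or that it favours AMPLEX. It does neither. Late visits add failures. The SAP also counts SAEs from the harvest procedure as procedure related, so ABG has an extra source of events, and with equally early visits ABG could lose more counted failures.

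Finally, the sizes rest on assumed rates. Many of the procedure-related events listed in protocol Appendix 1 are perioperative, which would make the late hazard lower than assumed, although interventions to promote fusion may come later.

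The events do appear in the safety tables (SAP 10.2 and 10.3), but that does not change the subject's SPC or CT status.

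**Conclusion.** The point holds in a limited form. Both confirmatory endpoints score a subject as free of an event up to Week 52 when the database holds such an event after an early assessment and by Day 365, and no planned analysis shows the effect.

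The effect is probably small: about 0.8 points of component risk for a Day 335 visit and 2.6 points at the Day 268 extreme, given a 10% one-year risk and constant hazard. At 5% and 15% risk the Day 335 figures are 0.4 and 1.1 points. Bias in the treatment difference needs visit timing or event rates to differ between arms. Its direction is unknown, and the shift is small against a 12-point margin. This is a cheap improvement to the derivation, not a threat to the trial's main conclusion.

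**What to change.** In SAP 9.2.1 and 9.3.1, count secondary interventions (and, in 9.2.1, device or procedure related SAEs) through the later of Day 365 and the date of the Week 52 assessment or CT. Score any recorded event in that period as failure for the Week 52 status. Keep the wide Table 1 window for the visit-based measures and CT only.

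State that this failure rule takes precedence over the missing-component rule. At present SAP 9.2.1 reads "If any of the components of the SPC at an analysis visit is missing, the SPC response status will be considered missing for the analysis". A known event combined with a missing score could therefore be replaced by an earlier success through LOCF.

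A hard stop at Day 365 for everyone looks simpler but would bring in a new error. A subject with an intervention on Day 420 and an assessment or CT on Day 440 could then count as a success on outcomes measured after the intervention. For CT fusion that goes against the requirement in protocol 7.2.1.2 and SAP 9.3.1 that bridging be achieved without such interventions.

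The cost is SAP wording and a small change to the derivation, with no new data and no change in sample size. The downside is minor: subjects assessed after Day 365 keep a slightly longer exposure period. A subject who is assessed early and then withdraws also remains unobserved to Day 365, which no cut-off rule can repair.

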### 2.2 Endpoints

#### 2.2.1 Primary Efficacy Endpoint

The primary efficacy endpoint is the proportion of subjects who meet all the following criteria for the Subject Performance Composite (SPC) Endpoint at 52 weeks:

- Improvement in pain on weight-bearing at fusion site ( $\geq 20$  mm reduction from baseline on 100 mm VAS)
- Absence of significant graft harvest site pain ( $< 20$  mm on 100 mm VAS)
- Improvement in Foot and Ankle Ability Measure Activities of Daily Living subscale (FAAM-ADL) ( $\geq 8$  points improvement from baseline)
- Absence of device related or procedure related SAEs (up to Week 52)
- Absence of secondary surgical or nonsurgical interventions intended to promote fusion (up to Week 52)

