### 9.9 Handling of Missing Data

For the primary and key secondary analyses, the imputation method of LOCF will be used in subjects with an unknown outcome.

Sensitivity analyses of missing data will be performed by utilizing the following imputation methods:

- 1) “missing-equals-failure”
- 2) multiple imputation methods

- 3) a tipping point analysis will be performed for the primary and key secondary efficacy endpoints which will allow assessment of sensitivity without need for postulating any missing data mechanism. For this analysis, all possible combinations of missing data from the two arms will be considered, and the point at which significance is no longer achieved will be identified.

The planned sensitivity analyses for the primary and key secondary endpoints will be described in further detail in the Statistical Analysis Plan (SAP).

All data collected on safety or adverse events will be reported to the extent it is available, regardless of the active/withdrawn status of participants.

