For the primary analysis, the last available SPC response status will be used (i.e., the last observation carried forward; LOCF) if the SPC response status at 52 weeks is missing. If no SPC response status data are available at previous visits, the SPC response status at 52 weeks will be considered failure.

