9.2.2 Sensitivity Analysis

The following sensitivity analyses will be conducted to assess the robustness of the primary analysis:

- As-treated analysis based on actually received treatment on the mITT analysis set
- Analysis on the ITT analysis set
- Analysis on the PP analysis set

The same analysis conducted for the primary analysis will be repeated for these sensitivity analyses.

In addition, sensitivity analyses using the following approaches for the handling of missing data will be conducted:

- Missing-equals-failure approach
- Multiple imputation
- Tipping point analysis

Missing-equals-failure approach:

All subjects with missing SPC status at 52 weeks will be considered failures.

Multiple imputation methods:

The missing data for each component of the SPC for 12, 24, and 52 weeks will be imputed sequentially by regression-based imputation models using treatment group, baseline characteristics, and outcomes from preceding visits as predictors. The missing SPC response status will be calculated based on the imputed data. This imputation procedure will be repeated 100 times, and the primary analysis method will be applied to each of the imputed datasets. A combined estimate of the difference of the proportions (AMPLEX minus ABG) and the corresponding two-sided 90% CI will be obtained by the methods described in Rubin (1987) (3).

Tipping point analyses:

Let n_{1m} and n_{2m} be the number of subjects with missing SPC response status at 52 weeks in AMPLEX and ABG group, respectively. The tipping point analysis will assess the non-inferiority in all possible combinations of missing data imputation (i.e., $(n_{1m}+1)*(n_{2m}+1)$ imputations), and the result will be presented graphically. Specifically, the horizontal and vertical axes of the graph will be the number of subjects imputed as success in AMPLEX group (i.e., ranges between 0 and n_{1m}) and the number of subjects imputed as success in ABG group (i.e., ranges between 0 and n_{2m}), respectively. The non-inferiority outcome (i.e., supportive or not supportive) will be plotted for each combination of the number of successes from each group in the graph by different symbols (e.g., a solid circle for supportive and an open circle for not supportive outcomes). Note that each result with the LOCF method (i.e., primary analysis) and with the missing-equals-failure approach will be represented as one of the combinations in the graph.

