9.3 Secondary Endpoint(s)

9.3.1 Key Secondary Endpoint

The key secondary efficacy endpoint will be the proportion of subjects who meet the following criteria for the CT radiographic fusion success at 52 weeks:

- Radiographic evidence of fusion by CT scan ($\geq 50\%$ bone bridging across the joint space for the full complement of joints in the absence of secondary surgical or nonsurgical interventions intended to promote fusion)

Non-inferiority of AMPLEX to ABG will be claimed if the lower bound of the 2-sided 90% CI for the difference of the proportions (AMPLEX minus ABG) is greater than -12.0%. The superiority will be claimed if the lower limit of the 2-sided 95% CI is greater than zero. The CI will be constructed with the normal approximation to the binomial.

A subject will be considered a CT radiographic fusion success if he/she has $\geq 50\%$ bone bridging across the joint space by the CT scan for all treated joints without secondary surgical or nonsurgical interventions intended to promote fusion, otherwise, the subject will be considered a CT radiographic fusion failure. The CT radiographic fusion response status will be determined for 12, 24, and 52 weeks. The response status will be assessed for each time point based on the windowed analysis visits. The response status for the absence of secondary interventions to promote fusion will be assessed in a period up to the actual visit date that the corresponding CT images for a particular analysis visit were collected. If any of the components of the CT radiographic fusion success criteria at an analysis visit is missing, the response status will be considered missing for the analysis visit.

For the key secondary analysis, the last available CT radiographic fusion response status will be used (i.e., the last observation carried forward; LOCF) if the response status at 52 weeks is missing. If no CT radiographic response status data are available at previous visits, the response status at 52 weeks will be considered failure.

The same set of sensitivity analyses as for the primary endpoint will be conducted for the key secondary endpoint. These sensitivity analyses will be conducted regardless of the testing results of the primary efficacy endpoint. Therefore, no multiplicity among sensitivity analyses will be adjusted.

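### A subject already known to have failed can be scored a Week-52 success, because one missing component makes the whole composite missing and an earlier success is then carried forward

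*SAP*

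**What the plan says.** SAP 9.2.1 determines SPC status at Weeks 12, 24 and 52. A subject who meets all criteria is a success; "otherwise, the subject will be considered an SPC failure". A later sentence in the same section covers incomplete data: "If any of the components of the SPC at an analysis visit is missing, the SPC response status will be considered missing". The primary test then fills a missing Week-52 status by LOCF: "the last available SPC response status will be used (i.e., the last observation carried forward; LOCF) if the SPC response status at 52 weeks" (the condition being that this status is absent). A subject with no earlier status is a failure.

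SAP 9.3.1 repeats this for the key secondary endpoint: "If any of the components of the CT radiographic fusion success criteria at an analysis visit is missing, the response status will be considered missing". LOCF follows, again with failure when there is no earlier status.

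For the two event components (related SAEs and fusion-promoting interventions), SAP 9.2.1 says status "will be assessed in a period up to the actual visit date that the corresponding visit-based variables for a particular analysis visit are collected". Protocol 2.2.1 runs both components to Week 52. Protocol 9.9 says that "the imputation method of LOCF will be used in subjects with an unknown outcome".

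**The concern.** SPC success is an all-components condition. Once one component is observed to fail, no value of the others can change the result, so the outcome is known. The SAP nevertheless calls it missing and replaces it with the last composite status. If that status was a success, a known failure enters the primary test as a success. The masked failure can be a related SAE or a repeat operation to obtain fusion, which the composite exists to count.

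The rule inflates the success rate of whichever arm is affected, in both tested endpoints. The bias in the difference can go either way. Masking in AMPLEX favours non-inferiority, and masking in ABG works against it. ABG also has one more component, harvest-site pain, that can be missing.

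**Working it through.** **1. Trace of the rule**

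| Earlier status | Week-52 data | Correct result | SAP result |
|---|---|---|---|
| SPC success, Week 24 | Pain reduction under 20 mm; FAAM-ADL missing | Failure | Missing, then LOCF success |
| SPC success, Week 24 | Related SAE or fusion-promoting surgery at Week 35; pain VAS missing | Failure | Missing, then LOCF success |
| CT fused, Week 24 | Later intervention to promote fusion; no Week-52 CT | Failure | Missing, then LOCF success |
| CT fused at both joints, Week 24 | One joint below 50% bridging, the other unreadable | Failure | Missing, then LOCF success |
| Failure, or no status | Any of the above | Failure | Failure |

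The error is therefore confined to subjects whose last available status was a success and whose failure came afterwards. If no Week-52 visit-based variable was collected, SAP 9.2.1 gives no end date for the event period, so it is unclear whether a recorded SAE or intervention counts as observed. On either reading the composite is missing and the earlier success is carried forward.

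**2. The plan's own figures**

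Inputs (SAP 3.2, Protocol 9.1): 60% ABG, 62% AMPLEX, margin 12 points, one-sided 5%, 85% power, 2:1 allocation.

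ABG n = (1.645 + 1.036)² × (0.62×0.38/2 + 0.60×0.40) / (0.02 + 0.12)² = 7.19 × 0.3578 / 0.0196 = 131.2, rounded up to 132. The total is 396, as stated, with power 85.2%. The CT power of 79% to 83% also reproduces (79.1% and 83.0%). The sample size is not in dispute.

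**3. Effect of masked failures**

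Move k1 AMPLEX and k2 ABG failures to success, with 320 and 160 analysed:

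- p1 = AMPLEX rate + k1/320; p2 = ABG rate + k2/160; d = p1 − p2
- SE = √[p1(1−p1)/320 + p2(1−p2)/160]
- P(claim non-inferiority) = Φ((d + 0.12)/SE − 1.645)

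The counts k1 and k2 are assumptions. For SPC with true rates exactly at the margin (48% and 60%), k1 = 3 and k2 = 0 give p1 = 0.4894, d = −0.1106, SE = 0.0478, and Φ(0.0094/0.0478 − 1.645) = 7.4%. The CT columns set ABG at 70% or 75% (Protocol 9.1) and AMPLEX 12 points lower.

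| Masked AMPLEX : ABG | SPC, 48% vs 60% | CT, 58% vs 70% | CT, 63% vs 75% |
|---|---|---|---|
| 0:0 | 5.0% | 5.0% | 5.0% |
| 3:0 | 7.4% | 7.5% | 7.6% |
| 6:0 | 10.5% | 10.9% | 11.3% |
| 6:3 | 5.0% | 5.0% | 5.0% |
| 3:3 | 3.3% | 3.2% | 3.1% |
| 0:3 | 2.1% | 2.0% | 1.9% |

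For SPC, 6:1 gives 8.3% and 6:4 gives 3.8%. Exact binomial enumeration of the SPC cases agrees within 0.1 point.

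The 6:3 row masks equal proportions of the two arms (6/320 = 3/160 = 1.9%). The difference is unchanged, but each arm's success rate is overstated by 1.9 points. If instead an equal share of true failures is masked, AMPLEX gains more, because at the margin it has more failures. The SPC error rate is then 5.5%, 6.4% and 8.2% at shares of 2%, 5% and 10%.

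**4. Power at the planned rates**

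At 62% vs 60% with 320/160, power is 90.6% with none masked, 95.8% at 6:0, 91.0% at 6:3 and 82.5% at 0:3.

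**5. A borderline trial**

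With ABG at 96/160, AMPLEX at 178/320 has a lower 90% bound of −12.2% and misses the margin; 179/320 has −11.9% and meets it. In that position one rescored subject changes the conclusion.

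**The case against.** - **The protocol can be read the SAP's way.** The synopsis and Protocol 9.6.2 apply LOCF to a missing Week-52 SPC endpoint and do not define when a composite with a missing component is missing. The SAP fills that gap, and its failure sentence can be read as a general definition that the later sentence qualifies. That is fair, and it makes the no-deviation statement in SAP section 12 arguable rather than plainly false. But Protocol 9.9 confines LOCF to unknown outcomes, and a subject with a failed component does not have one. Reading the later sentence as controlling is also exactly what produces the error.
- **Other analyses would reveal it.** Under missing-equals-failure in SAP 9.2.2, "All subjects with missing SPC status at 52 weeks will be considered failures". Component-level multiple imputation keeps an observed failure. Component summaries and the SAE and intervention tables would show the events, and the tipping-point grid contains the correct allocation as one of its points. All true, so the problem would not be hidden. But the claim rests on the LOCF analysis, and the grid also includes points where known failures are successes.
- **Few subjects would qualify.** A subject needs an earlier success, a later failure and a missing component. The questionnaires are completed at the same visit, and the Week-52 analysis window is wide (Day 268 to 456). This is a sound reason not to dwell on 6:0, which also needs no affected ABG subjects. It does not make the number zero: the plan allows about 15% discontinuation, and subjects who leave after an event are natural candidates.

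**Conclusion.** The concern holds. As written, the SAP scores some known failures as Week-52 successes in both the primary and the key secondary test. That conflicts with the all-components definition, with the event components running to Week 52, and with the protocol's restriction of LOCF to unknown outcomes.

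The existence of the error follows from the text alone. Its size rests on assumed counts. For three to six AMPLEX subjects with none in ABG, false non-inferiority on SPC is 7.4% to 10.5%. For equal proportions it stays at 5.0%, and for three ABG subjects alone it falls to 2.1%, with a loss of about 8 points of power at the planned rates. The direction cannot be known in advance. Because the rule misclassifies known outcomes in the analysis that decides the trial, it should be corrected before database lock.

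**What to change.** Replace the missing-component sentence in SAP 9.2.1 and 9.3.1 with an ordered rule:

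1. Failure if any applicable component is observed to fail. This includes any recorded fusion-promoting intervention up to Week 52 and, for SPC, any recorded device- or procedure-related SAE up to Week 52, even without a Week-52 visit.
2. Success only if all applicable components are observed and met.
3. Missing otherwise.

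Apply LOCF, multiple imputation and the tipping-point grid only to the third group.

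Two clarifications belong with this. State that the harvest-site component is not applicable when no harvest was done; Protocol 7.2.2.4 already treats it as an ABG-only outcome. Reconcile the visit-date event cutoff in SAP 9.2.1 with Week 52, and say which period applies when there is no Week-52 visit.

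The cost is SAP wording and programming. The sample size does not change, and no data are needed beyond those the endpoints already require. Adverse events are collected to final follow-up (SAP section 3), and Protocol 9.9 reports available safety data regardless of withdrawal. Protocol 8.1 does not class secondary surgical interventions as adverse events, so the programming must draw on the intervention records as well as the adverse event log. Observed success rates may be slightly lower.
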